7.2.1 Visit 1/Pre-Operative

Provide a description of what procedures will be performed on visit 1 or day 1 or pre-test in order of how these will be done. If your study only involves one session or visit, use this section only and indicate 7.2.2 as not applicable.

Preoperative (research related procedures only listed below):

- Eligibility screening
- Informed consent
- Randomization to study group
- Patient reported outcomes; 2 questionnaires

7.2.2 Visit 2 / Operative #1

Provide a description of what procedures will be performed on visit 2 or day 2 or post-test in order of how these will be done. If your study involves more than two sessions or visits replicate this section for each additional session or visit (e.g., 7.2.3, 7.2.4, etc.).

Operative Day #1:

- Cataract surgery with implantation of intraocular lens

Visit 3/1 Day #1

Provide a description of what procedures will be performed on visit 2 or day 2 or post-test in order of how these will be done. If your study involves more than two sessions or visits replicate this section for each additional session or visit (e.g., 7.2.3, 7.2.4, etc.).

One Day Post-Op #1:

- Standard of care visual acuity, intraocular pressure, and slit lamp examination

Visit 4 / 1 Week

Provide a description of what procedures will be performed on visit 2 or day 2 or post-test in order of how these will be done. If your study involves more than two sessions or visits replicate this section for each additional session or visit (e.g., 7.2.3, 7.2.4, etc.).

One Week Post-op #1

- Standard of care visual acuity, intraocular pressure, and slit lamp exam
- Standard of care manifest refraction

Visit 5 / Operative #2

Provide a description of what procedures will be performed on visit 2 or day 2 or post-test in order of how these will be done. If your study involves more than two sessions or visits replicate this section for each additional session or visit (e.g., 7.2.3, 7.2.4, etc.).

Operative Day #2:

- Cataract surgery with implantation of intraocular lens

Visit 6 / 1 Day #2

Provide a description of what procedures will be performed on visit 2 or day 2 or post-test in order of how these will be done. If your study involves more than two sessions or visits replicate this section for each additional session or visit (e.g., 7.2.3, 7.2.4, etc.).

One Day Post-op #2:

- Standard of care visual acuity, intraocular pressure, and slit lamp examination

Visit 7 / 1 Month

Provide a description of what procedures will be performed on visit 2 or day 2 or post-test in order of how these will be done. If your study involves more than two sessions or visits replicate this section for each additional session or visit (e.g., 7.2.3, 7.2.4, etc.).

One Month Post-op:

- Standard of care visual acuity, intraocular pressure, and slit lamp examination
- Standard of care manifest refraction
- Research related ETDRS visual acuity testing at distance, intermediate, and near, both monocularly and binocularly, uncorrected and best-distance corrected
- Standard of care dilated fundus examination

Visit 8 / 3 Month

Provide a description of what procedures will be performed on visit 2 or day 2 or post-test in order of how these will be done. If your study involves more than two sessions or visits replicate this section for each additional session or visit (e.g., 7.2.3, 7.2.4, etc.).

Three Month Post-op:

- Standard of care visual acuity, intraocular pressure, and slit lamp examination
- Research related ETDRS visual acuity testing at distance, intermediate, and near, both monocularly and binocularly, uncorrected and best-distance corrected
- Binocular defocus curve testing (visual acuity testing through blur)
- Patient un-blinding

- Patient reported outcomes; 2 questionnaires

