1.0 Objectives

1.1 Study Objectives

Describe the purpose, specific aims or objectives. State the hypotheses to be tested.

The purpose of this study is to compare the binocular distance, intermediate, and near visual acuity and patient reported outcomes of the Alcon Vivity and Bausch & Lomb enVista IOLs.

We hypothesize that the Alcon Vivity and Bausch & Lomb enVista IOLs will have similar distance, intermediate, and near visual acuity.

(If the null hypothesis is rejected, then the visual performance of the IOLs may be different).

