7.1 Study Design

Describe and explain the study design.

This is a prospective, single-center, patient and assessor-blinded, double-arm clinical study. Subjects will be enrolled at the Penn State Eye Center. Eligible subjects must be anticipated to undergo bilateral sequential cataract surgery. Both eyes from each patient will be considered study eyes.

Candidate patients who give written consent to participate in the study will be enrolled and screened to determine study eligibility, then examined to obtain their medical and ophthalmic history and establish their baseline ocular condition. Qualified subjects will be randomized to receive one of two study devices in both eyes. Post-operatively, subjects will undergo examination at 4 protocol-specific visits at regularly scheduled intervals through 3 months post-operatively, as shown in **APPENDIX 1: SCHEDULE OF CLINICAL ASSESSMENTS/PROCEDURES**.

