7.2 Study Procedures

Provide a step by step description of all research procedures being conducted (broken down by visit, if applicable) including such information as below (where and when applicable); describe the following:

- **HOW:** (e.g., data collection via interviews, focus groups, forms such as surveys and questionnaires, medical/school records, audio/video/digital recordings, photographs, EKG procedures, MRI, mobile devices such as electronic tablets/cell phones, observations, collection of specimens, experimental drug/device testing, manipulation of behavior/use of deception, computer games, etc.)
- **WHERE:** (e.g., classrooms, labs, internet/online, places of business, medical settings, public spaces, etc.)

All potential participants will complete all of the pre-operative assessments as part of Standard of Care treatment. At that time, the Principle Investigator will introduce the study to the potential participants and go over each lens that could be implanted. If patient agrees to move forward with study participation, the coordinator will complete screening and perform the consent process. The study participants will be provided two questionnaires to complete that ask about how much difficulty they presently have seeing things at distance, intermediate and near. It will also assess which specific visual disturbances (eg blurry vision, glare) they are experiencing before surgery takes place.

Randomization, the IOL randomization code list will be provided by the Dept. of Public Health Sciences. This determines which IOL would be implanted for each patient and will be assigned once the consent is

signed and it is determined that the subject has met all eligibility criteria. The PI will be unblinded to the lens that will be implanted as he will be doing the surgical procedure.

Post-operative assessments that occur for eye #1- Day 1 and week 1 as well as eye #2- Day 1 will be performed by [name] as part of standard of care. During this time, if an AE or SAE is identified, it would be reviewed and causality/IOL relationship will be determined by another Ophthalmologist, [name] who will be unblinded. At the 1 month and 3 month follow-up visits, assessments would be performed by the Blinded investigator, [name]. At study completion, after all study procedures are completed the coordinator will then pull the subject envelope containing the wallet card that reveals which IOL lens was implanted in both the right and left eye.

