8.3 Statistical methods

Describe the statistical methods (or non-statistical methods of analysis) that will be employed.

Descriptive data will be used for demographic characteristics as well as visual and refractive outcomes. A Shapiro-Wilk test will be used to assess the normality of the data. Visual acuities will be converted to logMAR notation to facilitate averaging and analysis.

The paired sample t-test or nonparametric Wilcoxon signed-rank test will be used to compare monocular and binocular visual acuity under uncorrected and distance-corrected conditions. Comparisons between patients with different IOLs will be evaluated with independent sample t-tests or the nonparametric Mann-Whitney test for visual acuity and refractive outcomes, depending on the normality of the data. The level of significance will be set at $p < 0.05$.

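### The Visit 8 list puts patient un-blinding before the questionnaires, against section 7.2, and the patient-reported comparison named in the purpose has no endpoint or analysis

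*Combined protocol and SAP*

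**What the plan says.** Section 7.1 describes the trial as "patient and assessor-blinded". Section 1.1 gives its purpose as comparing distance, intermediate and "near visual acuity and patient reported outcomes of the Alcon Vivity and Bausch & Lomb enVista IOLs".

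Two questionnaires are given. The section 7.2 narrative says that before surgery they cover difficulty seeing at distance, intermediate and near, and "which specific visual disturbances (eg blurry vision, glare) they are experiencing before surgery takes place". Table 1 schedules patient-reported outcomes at Visit 1 and Visit 8 only.

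On when the patient learns the lens, there are two statements:

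- The section 7.2 narrative: "after all study procedures are completed the coordinator will then pull the subject envelope containing the wallet card".
- The Visit 8 / 3 Month list, fourth and fifth of five items: "Patient un-blinding", then "Patient reported outcomes; 2 questionnaires". The template prompt above that list asks for procedures "in order of how these will be done".

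On endpoints and analysis, sections 1.2 and 1.3 list acuity, defocus-curve and refractive endpoints only. Section 8.3 compares the lenses with "independent sample t-tests or the nonparametric Mann-Whitney test for visual acuity and refractive outcomes, depending on the normality of the data". Section 9.7 repeats that test for the safety review and adds nothing for questionnaires.

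**The concern.** Patient masking matters most for what patients report themselves. Here they have what they need to form lens-specific expectations: under section 7.2 the principal investigator goes over each lens before consent, and under section 10.0 the risk of visual disturbances is explained in the consent form and again verbally. A patient who has just learned which lens was implanted may rate glare, haloes or reading difficulty differently.

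Visit 8 is the only post-operative collection of these ratings. If un-blinding comes first there is no masked rating to fall back on, and the step cannot be undone.

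The second gap does not depend on the first. Even with masking intact, the plan does not say which score is compared between lenses or how. That part of the purpose has no planned answer, and the items and summary could be chosen after the data are seen.

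**Working it through.** The plan gives no figure to reproduce on this point. The main check sets the texts side by side; the arithmetic is for scale only.

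**1. Order at Visit 8.** The list runs: standard-of-care examination, ETDRS acuity, defocus curve, un-blinding, questionnaires. Table 1 marks the questionnaires as research procedures at Visit 8, so they fall under the section 7.2 rule that all study procedures come first. Both orders cannot hold. Acuity and defocus testing precede un-blinding in either reading, so the primary endpoint (binocular distance-corrected intermediate acuity at 3 months) is not exposed.

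**2. How far the list can be trusted as a sequence.** Not far. The Visit 8 list omits the manifest refraction and adverse event monitoring that Table 1 schedules there, and the Visit 1 list omits the urine pregnancy test. Table 1 is no evidence of sequence either: its un-blinding row stands above the patient-reported row, but its last row is the pregnancy test, done only at Visit 1. The finding is therefore a contradiction to reconcile, not proof that un-blinding will come first.

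**3. Coverage of patient-reported outcomes.**

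| Place | Patient-reported outcomes? |
|---|---|
| 1.1 purpose | Yes, compared between lenses |
| 1.1 hypothesis | No |
| 1.2 primary endpoint | No |
| 1.3 secondary endpoints | No |
| 8.3 descriptive summaries | No (demographic, visual and refractive) |
| 8.3 between-lens tests | No (visual acuity and refractive) |
| 7.2 and Table 1 | Collected at Visits 1 and 8; instruments and scoring not given |

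**4. Scale.** Inputs: 3-4% of patients with severe or very bothersome disturbances, from a trial of similar lenses (section 10.0); 28 per arm planned and 22 per arm stated as required (section 8.2). Assumption: the disturbance questionnaire grades severity or bother, which the documents do not state.

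| | 28 per arm | 22 per arm |
|---|---|---|
| Expected cases at 3% | 0.03 × 28 = 0.84 | 0.03 × 22 = 0.66 |
| Expected cases at 4% | 0.04 × 28 = 1.12 | 0.04 × 22 = 0.88 |
| Shift from one changed rating | 1/28 = 3.57 points | 1/22 = 4.55 points |
| Exact (Clopper-Pearson) 95% CI for one event | 0.09% to 18.35% | 0.12% to 22.84% |

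The exact limits for 1 event in n are the 2.5% quantile of Beta(1, n) and the 97.5% quantile of Beta(2, n − 1).

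One altered rating is about as large as the whole quoted rate, and the intervals are wide. Such items support estimates with intervals better than a test.

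**The case against.** The strongest reply is that section 7.2 already settles the order: it is an explicit timing rule, whereas the visit list supports only an inference from bullet order. The prompt asking for chronological order is institutional template text, left unedited above Visit 8, and the lists are incomplete elsewhere. Section 15.5 also requires documented training of the study team. This is why the consequence is stated conditionally. It does not remove the contradiction: the visit list is the natural thing to consult on the day, and it says the opposite of the rule.

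Second, the arithmetic does not measure the bias. That is correct. The 3-4% comes from similar lenses, not these two arms, and the granularity of 1 in 28 would be the same under perfect masking. The figures show only how little it takes to move such an item.

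Third, section 7.0 has subject-facing materials uploaded separately and keeps actual survey questions out of the protocol, so the instruments may be defined in files not seen here. The reference list also includes a paper on the VF-14, a functional-impairment index for cataract. Neither fills the gap: section 7.0 does not bar naming an instrument or its score, and the body never links that reference to either questionnaire.

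Finally, the ordering and the missing endpoint are separate matters, and the second is closer to missing detail. They are kept together because both bear on the same part of the purpose, but the ordering point stands without the other.

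**Conclusion.** The concern holds. The Visit 8 list and the section 7.2 narrative give opposite orders for un-blinding and the questionnaires. If the list is followed, the only post-operative patient-reported ratings in a patient-blinded trial are given un-blinded. Whether that would happen in practice is not known, and the size of any resulting bias cannot be derived from the documents. The scale figures (about one expected case per arm, 3.6 to 4.5 points per changed rating) rest on the assumption that severity or bother is graded.

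The omission is also plain on the text: patient-reported outcomes are in the purpose but have no endpoint, named instrument, scoring or between-lens comparison. The primary endpoint and the listed secondary endpoints are unaffected. This should be corrected before any patient reaches Visit 8, but it does not threaten the trial's main conclusion.

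**What to change.** **Order.** In the Visit 8 list, put both questionnaires before un-blinding. Add one sentence that un-blinding takes place only after the questionnaires and all acuity and defocus testing are complete, in line with section 7.2, and put a matching note under Table 1.

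**Endpoint and analysis.** In section 1.3, add the 3-month result of each questionnaire as a secondary or exploratory endpoint, naming the instrument and its scoring. In section 8.3, compare the lenses by a method suited to the scale:

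- continuous score: mean difference with 95% CI, adjusted for the pre-operative score already collected;
- ordinal score: the Mann-Whitney test already named in section 8.3;
- yes/no or categorical disturbance items: counts and proportions per arm, with the difference and its 95% CI.

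If no between-lens comparison of these outcomes is intended, narrow section 1.1 instead.

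**Cost.** Two lines re-ordered, one sentence and one table note; then either a few endpoint lines and a short analysis paragraph, or a shorter purpose statement. No new data, visits or patients.

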7.3 Duration of Participation

Describe how long subjects will be involved in this research study. Include the number of sessions and the duration of each session - consider the total number of minutes, hours, days, months, years, etc.

The duration of each subject's study participation is estimated to be approximately 18 weeks; however, duration of participation is affected by the time lapse between the Pre-operative Visit, which may occur between Day -30 and Day 0, and the Operative Day #1 Visit on Day 0. Each subject will be followed for approximately 12 weeks after the Operative Visit #2.

8.0 Subject Numbers and Statistical Plan

8.1 Number of Subjects

Indicate the maximum number of subjects to be accrued/enrolled. Distinguish between the number of subjects who are expected to be enrolled and screened, and the number of subjects needed to complete the research procedures if applicable (i.e., numbers of subjects excluding screen failures.)

70

8.2 Sample size determination

If applicable, provide a justification of the sample size outlined in section 8.1 to include reflections on, or calculations of, the power of the study.

The FDA Summary of Safety and Effectiveness Data on the Alcon Vivity IOL compared the Alcon Vivity IOL to the Alcon Acrysof IQ SN60WF. It demonstrated binocular DCIVA's of 0.054 (SD = 0.09) and 0.196 (SD 0.113) logMAR units, respectively (Table 25; difference of 0.142). The difference between the DCNVAs was similar.⁸ We hypothesize that the neutral asphericity of the B&L enVista IOL will result in a slightly improved DCIVA and DCNVA as compared with that of the SN60WF. As such, we assumed that the mean difference in the DCIVA or DCNVA between the two study devices will be ≥ 0.12 logMAR units and that the standard deviation on these measurements will be approximately 0.10.^{8,11}

A 2019 ASCRS abstract by [name] also described the MX60E as having monocular UCIVA and UCNVA of 0.17 ± 0.17 and 0.44 ± 0.33 D, respectively.¹² Binocular UCIVA and UCNVA for the Alcon Vivity IOL was 0.058 ± 0.083 and 0.208 ± 0.104 D, respectively (monocular logMAR not reported).⁸ Although monocular and binocular acuities are not typically compared, the difference between the Vivity and MX60E IOLs might be approximately 0.11 for intermediate and 0.24 logMAR units, based upon this above information. The higher SDs are likely due to the uncorrected astigmatism in this population.

The sample size calculation was performed using <http://clincalc.com>. Based on a difference in binocular DCIVA of 0.12 logMAR units and a SD of 0.10, we calculated that for an α of 0.05 and power of 0.80, 22 bilaterally implanted patients would be required in each group. However, 28 patients were included to more closely approximate a normal distribution and ensure adequate numbers after accounting for screen failures and patients lost to follow-up.

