3.1 Inclusion Criteria

Create a numbered list of the inclusion criteria that define who will be included in your final study sample (e.g., age, gender, condition, etc.)

Each of the following criteria must be met for study participation:

1. Male or female, age 18 or older at the time of study enrollment.
2. Visually significant cataract in the study eyes for which phacoemulsification cataract extraction and posterior chamber IOL implantation is indicated.
3. Anticipated to undergo bilateral sequential cataract surgery
4. Projected postoperative CDVA 0.20 logMAR (Snellen 20/32) or better in the study eyes, as determined by an Investigator's medical judgement.
5. Calculated spherical power targeted at emmetropia at distance in the study eyes.
6. Calculated IOL power between +10.0 - +30.0 D, inclusive, in both eyes.
7. Measured against-the-rule astigmatism less than 0.6 D or with-the-rule/oblique astigmatism less than 1.25 D.
8. If wearing rigid gas permeable (RGP) contact lens in the study eye, willingness to discontinue lens wear for \geq 21 days prior to preoperative biometry.
9. Availability, willingness, and sufficient cognitive awareness to return for study-required visits and comply with examination procedures.
10. Willingness to sign the IRB-approved informed consent form (ICF) for study participation.

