15.2 Feasibility of recruiting the required number of subjects

Indicate the number of potential subjects to which the study team has access. Indicate the percentage of those potential subjects needed for recruitment.

We anticipate 20% of patients being seen for cataract evaluations will qualify for and ascent to participation in the research study.

The Principal Investigator will see an average of 10 cataract evaluations per week. It is estimated that this will generate 2 study subjects per week.

The Sponsor was advised that study recruitment would last 36 weeks. This is enough time to recruit as many as 72 study subjects, but only 56 subjects are to be enrolled.

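### Uncorrected acuity is compared between lenses without adjusting for baseline astigmatism, which every subject has measured; the tests are valid but may give up some precision on secondary endpoints.

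*Combined protocol and SAP*

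**What the plan says.** Section 1.3 lists mean uncorrected acuity at 4 m, 66 cm and 40 cm, each monocular and binocular, among the secondary endpoints. That makes six means. The primary endpoint in 1.2 is binocular intermediate acuity with distance correction in place.

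Section 3.1, item 7, sets the astigmatism limit: "Measured against-the-rule astigmatism less than 0.6 D or with-the-rule/oblique astigmatism less than 1.25 D". A value must therefore exist for every subject before surgery, and Table 1 schedules both biometry and corneal topography at Visit 1. Section 3.2, item 15, excludes planned limbal relaxing incisions, and the documents describe no other treatment of astigmatism at surgery.

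Section 8.2 quotes uncorrected acuities for the two lenses from outside sources and then remarks: "The higher SDs are likely due to the uncorrected astigmatism in this population".

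For the analysis, 8.3 says: "Comparisons between patients with different IOLs will be evaluated with independent sample t-tests or the nonparametric Mann-Whitney test for visual acuity and refractive outcomes", with the choice between them made on normality. No covariate, regression model or stratification by astigmatism appears anywhere in the document.

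**The concern.** The plan suggests a likely cause of spread in uncorrected acuity, holds a pre-randomization measurement of it on every subject, and leaves that measurement out of the comparison. If astigmatism predicts uncorrected acuity in this trial, the unadjusted comparisons carry avoidable noise. With 28 per group, the arms could also differ in astigmatism by chance, and no planned analysis would account for it. At stake are the width of the confidence intervals and the readability of six secondary endpoints. The primary result is not at stake.

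**Working it through.** **The plan's own sample size.** Section 8.2 takes its inputs as "Based on a difference in binocular DCIVA of 0.12 logMAR units and a SD of 0.10" and concludes that "for an α of 0.05 and power of 0.80, 22 bilaterally implanted patients would be required in each group". The normal formula, two-sided, gives n per group = 2 × (1.960 + 0.842)² × (0.10/0.12)² = 10.9, so 11 per group and 22 in total. The exact t-test gives 12 per group. The stated 22 matches the total. That is a separate matter. Here it shows only that the primary is amply powered at 28 per group (about 99%), so this point concerns secondary endpoints alone.

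**Inputs (all from 8.2, logMAR)**
- MX60E, monocular uncorrected intermediate: mean 0.17, SD 0.17.
- Vivity, binocular uncorrected intermediate: mean 0.058, SD 0.083.
- Vivity, binocular distance-corrected intermediate: SD 0.09.
- SD assumed for corrected acuity in sizing: 0.10.
- Group size: 28 before losses. Section 15.2 agrees, since "only 56 subjects are to be enrolled"; section 8.1 gives 70. Group size does not affect the percentages below.
- R² of uncorrected acuity on baseline astigmatism: not given, so a range is assumed.

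**Step 1: average variance.** (0.17² + 0.083²)/2 = (0.0289 + 0.0069)/2 = 0.0179, an SD of 0.134.

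**Step 2: excess over 0.10² = 0.0100.** For MX60E, 0.0289 − 0.0100 = 0.0189. For Vivity there is none (0.0069 is below 0.0100), so it is counted as zero. The average excess is 0.0189/2 = 0.00945. As a share of total variance, this is 0.00945/0.0179 = 0.53.

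**Step 3: assumed share due to baseline astigmatism.** A quarter gives R² = 0.13 and a half gives R² = 0.26.

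**Step 4: precision.** The standard error is multiplied by √(1 − R²), and the equivalent sample size by 1/(1 − R²).

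| R² | SE multiplier | SE reduction | Equivalent extra patients |
|---|---|---|---|
| 0 | 1.00 | 0% | 0% |
| 0.13 | 0.93 | 7% | 15% |
| 0.26 | 0.86 | 14% | 36% |

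If Vivity's shortfall is netted off rather than set to zero, the share in Step 2 is (0.0179 − 0.0100)/0.0179 = 0.44. R² is then 0.11 to 0.22, the SE reduction 6 to 12%, and the equivalent gain 12 to 28%.

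**Step 5: power.** The difference is 0.17 − 0.058 = 0.112; 8.2 rounds this to 0.11. With SD 0.134, 28 per group and two-sided 0.05, the formula Φ(0.112/(SD × √(2/28)) − 1.96) gives 0.88 unadjusted, 0.92 at R² = 0.13 (residual SD 0.125) and 0.955 at R² = 0.26 (residual SD 0.115).

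**Step 6: chance imbalance.** The standard error of the between-arm difference in astigmatism is √(2/28) = 0.27 SD. An imbalance of that size shifts the acuity difference by √R² × 0.134 × 0.267, or 0.013 to 0.018 logMAR, against about 0.11 anticipated.

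**Step 7: the like-for-like check.** Only one lens has uncorrected and corrected SDs under the same viewing condition: Vivity, binocular, 0.083 and 0.09. There is no excess, so on this pair the gain would be near zero. No SD is given for uncorrected distance acuity.

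**The case against.** The strongest case against is that an unadjusted two-sample test in a randomized trial is valid, and adjustment is an efficiency preference with an uncertain return. Most of this stands.

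- **A reader might infer that the plan calls astigmatism the source of spread in this trial's own endpoints.** It does not. The sentence in 8.2 follows SDs from cited data, most naturally refers to the cited abstract's patients, and is hedged. Inclusion 7 also narrows the range of astigmatism here.
- **A reader might infer that up to 65% of variance is recoverable,** from 1 − (0.10/0.17)² = 0.65. That sets a monocular uncorrected SD for one lens against an assumed binocular corrected SD, then applies it to both arms. Part of the gap may come from monocular testing, so 0.65 is not a bound the documents support. The 0.53 in the working still mixes monocular and binocular data and is illustrative only.
- **A reader might infer that imbalance biases the lens effect.** Randomization keeps the unadjusted estimate unbiased, and its standard error already covers chance imbalance. Adjustment removes the linear part of whatever imbalance occurs.
- **The covariate is imperfect.** Pre-operative astigmatism only partly predicts post-operative refractive astigmatism. Unsigned magnitude ignores axis, which inclusion 7 treats as relevant, and one common slope may fit poorly if the lenses tolerate astigmatism differently.

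These points reduce the expected gain. They do not argue for leaving the covariate out: if R² is near zero, adjustment costs one of 54 degrees of freedom (56 − 2).

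**Conclusion.** The point holds as a modest, free improvement. Section 8.3 leaves out an already measured baseline variable that 8.2 itself suggests is prognostic for uncorrected acuity. Nothing planned is invalid, and the primary and other distance-corrected endpoints are untouched.

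For uncorrected intermediate acuity, the standard error could fall by about 7 to 14%. This rests on two assumptions that the documents cannot confirm: that the averaged cited SDs carry over to this trial, and that baseline astigmatism explains a quarter to a half of the excess variance. The lower end is near zero, as the matched Vivity pair indicates. On the averaged variance, unadjusted power is already about 0.88 with all 28 per group, so the documents do not support calling these comparisons inadequate for lack of adjustment.

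**What to change.** Add to 8.3, in substance: each uncorrected acuity at 3 months (distance, intermediate and near; monocular and binocular) is compared between lenses by ANCOVA, with terms for lens and baseline astigmatism magnitude. The adjusted mean difference and its 95% CI are reported. The planned t-test or Mann-Whitney test is kept as a sensitivity analysis.

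The text should also settle three details:
- **Source.** Name the single pre-operative measurement used to apply inclusion 7, since Table 1 lists both biometry and topography.
- **Eye.** Use the mean of the two eyes for binocular outcomes and the same eye's value for monocular outcomes. How 8.3 handles a patient's two eyes in the monocular comparisons is a separate question that this covariate does not answer.
- **Timing.** Use the baseline value, not the post-operative refraction, which is measured after randomization.

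The cost is a short addition to 8.3 and one degree of freedom. No new measurement, visit or patient is needed.

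### Section 8.2's inputs give 11 to 12 patients per group for 80% power (13 to 14 with Mann-Whitney), not the stated 22; the error is conservative

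*Combined protocol and SAP*

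**What the plan says.** The calculation is in Section 8.2. The inputs are given as "Based on a difference in binocular DCIVA of 0.12 logMAR units and a SD of 0.10", with alpha 0.05 and power 0.80, and the result is that "22 bilaterally implanted patients would be required in each group". Just before this, 8.2 says that "the standard deviation on these measurements will be approximately 0.10". It prints the source binocular DCIVA values for the Vivity and SN60WF lenses: means 0.054 and 0.196 (difference 0.142), SDs 0.09 and 0.113. The planned 0.12 is the 0.142 reduced, because the enVista is expected to do slightly better than the SN60WF.

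A later step raises the number: "28 patients were included to more closely approximate a normal distribution and ensure adequate numbers after accounting for screen failures", and for loss to follow-up. Section 15.2 says that "only 56 subjects are to be enrolled", which is 2 x 28, so 28 is a per-group number, and so is the 22 it replaces.

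Section 8.3 gives the between-group test: "Comparisons between patients with different IOLs will be evaluated with independent sample t-tests or the nonparametric Mann-Whitney test". Neither sidedness nor the allocation ratio is stated.

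**The concern.** A difference of 0.12 against an SD of 0.10 is a standardised effect of 1.2, which is large. Two-group comparisons of that size need about a dozen patients per group for 80% power, so 22 per group looks about twice too high. The allowance for losses cannot explain the gap, because 8.2 applies it after the 22, in the step to 28.

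What is at stake is the sample size justification. Its one calculation cannot be reproduced from its own inputs, the power it claims for 22 per group is not the power the trial would have, and the explanation of the 28 starts from the wrong base.

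**Working it through.** **Inputs (Section 8.2).** Difference 0.12; SD 0.10, described as the SD of the measurements, so used as the common within-group SD; alpha 0.05; power 0.80. Assumed: two-sided test and 1:1 allocation.

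**Attempt to reproduce 22, normal approximation.**
n per group = 2 x (z for alpha/2 + z for power)^2 x (SD/difference)^2
= 2 x (1.960 + 0.842)^2 x (0.10/0.12)^2 = 10.90, so **11 per group, 22 in total**.

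**Independent t-test (noncentral t).** 11.94, so **12 per group, 24 in total**. Power is 76.3% with 11 and 80.2% with 12.

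**Mann-Whitney.** Divide the t-test n by the asymptotic relative efficiency:
- normal data: 11.94/0.955 = 12.5, so 13;
- lower bound: 11.94/0.864 = 13.8, so 14.

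**Other readings, per group.**

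| Change to the inputs | Normal | t-test |
|---|---|---|
| One-sided 0.05 | 9 | 10 |
| Larger source SD, 0.113 | 14 | 15 |
| Power 0.90 (not stated) | 15 | 16 |
| Alpha 0.025 (not stated) | 14 | 15 |

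None reaches 22. The settings tried that do come close change the stated alpha or power, for example two-sided 0.01 with 90% power (21 normal, 23 t-test).

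**Power for 0.12 at SD 0.10, two-sided t-test.**
- 22 evaluable per group: 97.3% (normal check: 0.12/(0.10 x sqrt(2/22)) = 3.98; 3.98 - 1.96 = 2.02, so 97.8%).
- 28 evaluable per group: 99.3%.

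**Difference detectable with 80% power at SD 0.10.** About 0.086 logMAR with 22 per group and 0.076 with 28.

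**Are the inputs or the n more likely wrong?** The root mean square of the printed SDs is sqrt((0.09^2 + 0.113^2)/2) = 0.102, which matches 0.10. The 0.12 is a stated reduction from 0.142. Both inputs therefore have visible support.

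**Where 22 could come from.** 2 x 10.90 = 21.8, so 22 is the two-group total. The same 21.8 arises per group if the SD is multiplied by sqrt(2). The document does not show which, if either, happened.

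**The case against.** The strongest defence is that nothing turns on the error. On the stated inputs the plan has more patients than it needs, 28 per group need not change, and no endpoint or analysis depends on the 22. That stands, and it limits the weight of the point. It does not make the stated figure correct.

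Four stronger readings might be inferred; the documents do not support them.

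- **The trial may be underpowered because the true SD was about 0.14.** At 0.12 that SD gives 21.4 by the normal approximation, but 0.14 appears nowhere in the document. By the t-test it gives 22.4, so 23 per group, with 79.3% power at 22. The uncorrected intermediate figures in 8.2 come nearest: difference 0.17 - 0.058 = 0.112, SDs 0.17 and 0.083, pooled 0.134. They set monocular against binocular acuity, are not the primary endpoint and are not named as inputs. The plan itself explains them: "The higher SDs are likely due to the uncorrected astigmatism in this population". Even on those figures, power with 28 evaluable is about 87%. Falling below 80% also needs a loss of about a fifth (22 of 28), and no loss rate is given.
- **The calculator's total was certainly misread as a per-group number.** This fits, but it is unproven.
- **The trial enrols 28/12 = 2.3 times too many patients.** This sets planned enrolment, which includes an allowance for losses, against a minimum of evaluable patients.
- **The 70 in Section 8.1 against the 56 in Section 15.2 is part of the same error.** The 70 could be a ceiling that counts screened patients. It deserves a clarifying sentence, but it does not enter this calculation.

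**Conclusion.** The point holds. The stated 22 per group is about twice the 11 (normal) or 12 (t-test) that the inputs require, and well above the 13 to 14 for Mann-Whitney. This rests on two assumptions, two-sided testing and equal groups; a one-sided test widens the gap. The per-group n is the figure most likely to be wrong, because the difference and the SD both agree with the source data in 8.2.

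The consequence is a justification that does not support its own number, not a shortage of patients. With 28 evaluable per group, t-test power for 0.12 stays at or above 80% up to an SD of about 0.157. The correction should be made because it is cheap and any reader with a calculator will find the discrepancy.

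**What to change.** Re-run the calculation, confirm sidedness and allocation ratio, and restate 8.2 along these lines:

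> To detect 0.12 logMAR in binocular DCIVA with a common SD of 0.10, two-sided alpha 0.05 and 1:1 allocation, the independent t-test needs 12 evaluable patients per group (24 in total) for 80% power; the Mann-Whitney test needs about 13 to 14 per group. We plan 28 per group (56 in total) to allow for losses and for an SD larger than assumed. T-test power for 0.12 is about 99% if all 28 are evaluable and 97% with 22; the differences detectable with 80% power are about 0.076 and 0.086 logMAR.

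Drop the argument that a larger n brings the data closer to normality: more patients do not change the shape of the acuity distribution.

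If other inputs were in fact entered to obtain 22 per group, state and source those instead. Do not choose an SD afterwards to fit 22.

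Cost: one calculation and a few sentences in 8.2. No extra patients, and no change to the planned 28 per group.
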